6.3.3 Secondary Outcome Analysis

6.3.3.1 Longitudinal analysis of the AGS scale

In secondary analysis, we will include historical controls in the GEE models described in section 6.3.2; the "age at treatment" (time zero) for controls will be their age at their final encounter. The GEE models will also adjust for confounders (e.g. age of the subject, length of disease, and genotype⁷⁵) especially variables that were identified as being related to receiving treatment (see Section 6.3.1). We will fit several working correlation structures to model the association between the repeated measurements on each patient, and will use goodness of fit criteria for GEE to choose between the structures. Goodness of fit criteria will also be used to compare fit of models (e.g. for models that include time as a continuous variable versus a series of indicator variables for visit).

In addition to GEE, we will fit quasi-least squares (QLS) regression models.⁷⁶ QLS is a computational approach for estimation of the correlation parameters in the framework of GEE that can be applied should GEE fail to converge, or to fit correlation structures that are not available in the framework of GEE. For example, the Markov correlation structure that is plausible for unequally spaced data is not available in the **xtgee** command for implemention of GEE in Stata.

In addition to the GEE analysis that includes historical controls, we will implement several sensitivity analyses that are described in the Table below. These methods were successfully implemented in analysis of our preliminary data.

Table 2. Statistical Approaches				
Question to be Evaluated in Sensitivity Analysis	Statistical Approach			
For each patient who was eventually treated, if we obtain their average of their AGS scale values prior to treatment (pre-treatment average) and the average of their AGS scale values after treatment (post- treatment average), are the post-treatment averages higher than the pre-treatment averages?	Compute the average of the within subject changes (post-treatment average minus pre-treatment average) with 95% CI; apply the paired t-test to compare the mean of pre-treatment to the mean of post-treatment averages within patients.			
Is the average AGS scale value higher after treatment than before treatment, when we modify the previous analysis to include patients who were never treated, by calculating their pre-treatment average AGS scale as the average of all of their AGS scale values?	GEE analysis in which patients who were treated contribute two measurements (pre-treatment average and post-treatment average), while patients who were never treated contribute one measurement ("pre-treatment" average of AGS scale). The GEE model will include an indicator variable for post-treatment and use an exchangeable correlation structure to account for the intra- subject correlation of measurements on each patient.			
Does the AGS scale at screening differ from the final value within patients?	Paired t-tests or non parametrics Wilcoxon signed-rank test will be applied as appropriate to compare the screening and final values within patients.			

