3.1.3 Allocation to Treatment Groups and Blinding

This is an unblinded, open-label study. A historical cohort will be used for comparison of the natural history of the AGS Scale.

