6.3 Statistical Methods

6.3.1 Baseline Data and Descriptive Analysis

Baseline and demographic characteristics will be summarized overall by standard descriptive summaries (e.g. means and standard deviations for continuous variables such as age and percentages for categorical variables such as gender). In addition, demographic characteristics and clinical variables that are evaluated at the first encounter will be compared between subjects who are never treated, versus those who are eventually treated. Patients are not randomized to receive treatment (or not), so it is important to identify variables that are associated with an increased (or decreased) likelihood of receiving treatment. Chi-square tests will be used to compare categorical variables between groups. T-tests or tests of medians (for skewed variables) will be used to compare continuous variables between groups. Overlaid histograms will also be used to evaluate the distribution of continuous baseline variables between patients who were never treated, versus those who were eventually treated. In addition, Kaplan-Meier analysis with the log rank test will be used to compare the distribution of time to treatment between levels of categorical variables (e.g. group genotype) measured at baseline. In our preliminary analysis, we did not identify meaningful differences between patients who were never treated, versus those who were eventually treated.

We will conduct descriptive statistical analysis using inferential and graphical secondary data analytic techniques. The primary and secondary assessments will first be summarized by time of measurement. In addition, individual "spaghetti" plots will be generated for each assessment. Changes in primary and secondary outcomes from baseline (with 95% confidence intervals [CI]) will be calculated at specified time points, e.g. between baseline and 52 weeks. In addition, overall changes (final minus baseline) (with 95% CI) will be computed for primary and secondary outcomes. In addition to means (with 95% CI) we will also calculate median changes (with 25th to 75th

percentiles). Analyses will be conducted in Stata 18.0, with a p-value < 0.05 as the criterion for statistical significance.

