6.3.2 Primary Outcome Analysis

As is often the case in a study of a rare disease, we face a number of challenges in our analysis. The number of available patients with AGS is limited, so that our sample size is small. This protocol grew out of a compassionate use trial, so that randomization could not be employed to assign patients to receive treatment (or not). The temporal spacing of measurements differs between treated patients versus historical controls. As a result of these features, there are limitations to many of the standard statistical approaches. Our approach will therefore be to apply a recommended approach for efficacy, but to also apply several sensitivity analyses. Our goal will be to demonstrate efficacy for several statistical approaches, as we achieved in our analysis of preliminary data.

Our efficacy analysis for our primary outcome will apply the method described in Section 15.4 of Fitzmaurice, Laird, & Ware⁷⁴ that decomposes longitudinal effects of treatment versus cross-sectional effects due to participants starting treatment at different ages. We will first create a time for each patient that is negative prior to treatment and is positive after treatment. We will then fit a GEE model that includes time within patients, an indicator variable for treatment and a time by treatment interaction term. If the interaction term is significant, this will indicate that the change over time in AGS score (slope) is different after treatment, versus before. If the interaction term is not significant, it will be removed and the model will be fitted with time and the indicator variable for (post) treatment. If the indicator variable differs significantly from zero, this will indicate that the AGS score is higher on average, post-treatment. To compare values at baseline and 52 weeks post baseline, different parameterizations of time (continuous versus indicator variables at different visits) will be considered and analyses will also be performed on data restricted to values measured at baseline and 52 weeks post baseline. This approach will first be applied to patients who are eventually treated. to compare their AGS scores pre versus post-treatment.

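### The control-inclusive GEE gives historical controls and treated patients one untreated slope, so a slope difference between the groups biases the treatment terms, in either direction

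*Combined protocol and SAP*

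**What the plan says.** Section 6.3.2 defines the model: "We will then fit a GEE model that includes time within patients, an indicator variable for treatment and a time by treatment interaction term". A significant interaction is read as a change of slope after treatment. Otherwise there is a second step: "If the interaction term is not significant, it will be removed and the model will be fitted with time and the indicator variable". On the population, it says "This approach will first be applied to patients who are eventually treated".

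Section 6.3.3.1 then makes the secondary step: "we will include historical controls in the GEE models described in section 6.3.2". A control's time zero is the age at the last encounter. The models also adjust for confounders such as age, disease length and genotype, and for variables found to be related to receiving treatment. No ever-treated indicator is named, and no interaction of group or of any confounder with time. QLS models are fitted alongside the GEE.

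The comparability check in section 6.3.1 sets never-treated patients against those who later receive the drug: "demographic characteristics and clinical variables that are evaluated at the first encounter will be compared between subjects who are never treated, versus those who are" (sentence cut here). Section 3.1.3 gives the role of the controls: "A historical cohort will be used for comparison of the natural history of the AGS Scale". Section 6.4 expects still more power from the data set with the controls (more than 50 of them).

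**The concern.** Control records all lie at or before time zero, so they inform only the untreated level and slope. The interaction then compares the treated patients' post-treatment slope with a blend of two populations' untreated slopes, and section 6.3.2 would read any difference as a change brought by treatment.

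The planned safeguards do not separate the two slopes. The section 6.3.1 comparison uses first-encounter variables, which say nothing about slope, and its preliminary finding of no meaningful differences reports no slope. Confounders entered as main effects shift levels, not slopes. The plan does write out group by time terms elsewhere: cohort by time for the GMFM-88 (6.3.3.2) and a three-way term for source study (6.3.3.6). It has none for treated versus control.

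At stake is how the control-based result is read. Section 2 announces a comparison with historical controls, and section 6.3.2 aims to show efficacy under several approaches, so a biased pooled result could be counted as added support.

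**Working it through.** **1. The plan's own figures.** Paired t-test, 30 pairs, effect size 0.77, two-sided alpha 0.05: noncentrality 0.77 x sqrt(30) = 4.22 on 29 df gives power 98.27% (plan: 98.3%). Effect size 0.53 gives 80.1% (plan: 80%), and 0.53 x 1.04 = 0.55. These reproduce. They concern within-patient change in treated patients; no figure is given for the control-inclusive GEE.

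**2. Bias formula.** Write the mean as b0 + b1·t + b2·T + b3·t·T, with T = 1 after treatment. Controls have T = 0 throughout. Let sT and sC be the untreated slopes of treated patients and controls, and assume no drug effect. With balanced visits and strongly correlated values within a child:

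- b1 estimates w·sC + (1 - w)·sT, where w = nC·SC / (nC·SC + nT·ST) and S is the sum of squared deviations of one child's pre-zero visit times.
- The interaction therefore tends to w·(sT - sC), not 0.
- In the second step (one common slope), the indicator tends to w*·(sT - sC)·D. D is the gap between mean post- and mean pre-treatment visit time in treated patients, and w* is w with the treated post-treatment spread added to the denominator.

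Both are zero only if sT = sC, and both change sign with the slope difference.

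**3. Numbers for one assumed design.** From section 6.4: 45 treated, 50 controls. Assumed, because the documents do not give them: treated visits at -2 to 0 years by 0.5 and at 3, 6, 9 and 12 months; control visits at -3 to 0 years by 0.75; sT = 0.

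- Controls: 50 x 0.75² x 10 = 281.25. Treated, pre: 45 x 0.5² x 10 = 112.5. Treated, post: 45 x 0.25² x 5 = 14.06.
- w = 281.25/393.75 = 0.714; w* = 281.25/407.81 = 0.690; D = 0.625 + 1 = 1.625.

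| Control slope (points/year) | Interaction: formula / simulated | Indicator: formula / simulated |
|---|---|---|
| -0.1 | +0.07 / +0.07 | +0.11 / +0.11 |
| -0.25 | +0.18 / +0.17 | +0.28 / +0.27 |
| -0.5 | +0.36 / +0.37 | +0.56 / +0.56 |
| +0.25 | -0.18 / -0.21 | -0.28 / -0.28 |

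The +0.56 at -0.5 equals the size (0.55) that the plan says it has 80% power to detect.

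If treated children have only two pre-treatment values (-0.5 and 0 years), w = 281.25/(281.25 + 45 x 0.125) = 0.98, so controls supply almost the whole reference slope. Appendix 2 schedules one pre-treatment AGS assessment, at screening; any others depend on scoring past records.

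**4. False-benefit rates with no drug effect.** All sets use 45 treated, 50 controls and robust standard errors. Set A counts a significant interaction. Sets B and C count benefit at either step of the two-step test.

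| Set and main assumptions | Control slope: rate | With ever-treated and ever-treated x time |
|---|---|---|
| A: between-child SD 4; slope/residual SD 0.5/0.7 or 0.3/1.2; 4 control values over 1.5 years; 800 runs | 0: 5-7%; -0.1: 6%; -0.2: 10-20%; -0.3: 19-36%; -0.5: 43-70% | 4-6% |
| B: design of step 3; SDs 3, 0.2, 0.75; 400 runs | 0: 4%; -0.1: 23%; -0.25: 74%; -0.5: 100% | 5-6% |
| C: SDs 3, 0.3, 1.0; four (or two) pre-treatment values; 300 runs | 0: 6% (5%); -0.2: 13% (24%); -0.3: 24% (32%); -0.5: 61% (66%) | 3-7% |

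In set B the treated-only fit stays at 5-6% throughout. At a control slope of +0.25 the pooled model declared benefit in 0% of runs.

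**5. What drives the bias and what repairs it.** In the set B design:

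- An ever-treated main effect alone leaves 24%, 74% and 100% at -0.1, -0.25 and -0.5. The term that matters is ever-treated by time.
- Controls 1.5 points lower with equal slopes gave 4%; both groups declining at -0.25 gave 6%. The slope difference is the cause, not level or decline as such.

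**The case against.** The strongest case is about reach. The primary fit is treated-only, as are the paired comparisons in Table 2, and control slopes cannot bias any of them. The affected model is labelled secondary, and section 6.4 calls the secondary analyses mainly hypothesis-generating. Since the treated-only and control-inclusive models are both fitted, contamination would show as disagreement. The spaghetti plots might show it too, and the confounder list is open-ended. This limits the consequence and stands. It does not remove the point: the plan has no rule for reading such a disagreement, and nothing guarantees a group by time term.

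Direction and size are also fair objections. No control slope is documented. Section 1.1 describes both subacute skill loss and a later apparent burning-out, so either sign is possible. The simulated rates differ widely, and none of the sets models the floor or ceiling of the scale. This stands too.

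A third objection is that ever-treated by time makes controls nearly uninformative and so undoes the planned natural-history comparison. This is why the pooled model should be kept and reported beside the extended one.

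A reader might infer that controls must decline faster because new recruits pass the section 3.3.3 exclusions and no screen is stated for controls. The documents do not support that. Section 3.3.1 exempts patients transferred from the compassionate-use study, section 6.3.3.6 also brings in data from patients who did not transfer, and nothing links those exclusions to AGS-scale slope.

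**Conclusion.** The point holds for the secondary control-inclusive GEE/QLS models only. As specified, they assume that treated patients and historical controls have the same untreated slope, and neither the baseline comparison nor main-effect adjustment tests this. If the assumption fails, the interaction and the follow-on indicator are biased by an amount proportional to the slope difference, toward or against benefit according to its sign.

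That structure follows from the text. The size does not: for assumed control slopes of -0.2 to -0.5 points per year against stable treated patients, false benefit ran from about 10% to 100%, depending on visit pattern, variances and which test is counted. With the two added terms it was about 5% in every set. In set A a difference of 0.1 per year caused no visible inflation; in set B it gave 23%.

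It would be wrong to conclude that the primary efficacy result is inflated, or that the bias is known to favour the drug.

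**What to change.** In section 6.3.3.1:

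- Fit the control-inclusive GEE/QLS models also with an ever-treated indicator and an ever-treated by time term.
- Report the ever-treated by time estimate with its 95% CI, as the check on whether controls are a usable slope benchmark.
- Report the treatment contrast from that model beside the pooled-slope contrast.
- State that the pooled result, and the section 6.4 expectation of greater power as it applies to this model, depend on equal untreated slopes.
- State that if the two models disagree, the pooled result is not read as independent support for efficacy.

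The cost is wording, two model terms and one reported interval; no new data are needed. The downside is precision: with the added terms, controls contribute little to the slope-change test, and power falls to about that of the treated-only analysis. What is given up is the precision gained by assuming equal slopes. Screening controls by the section 3.3.3 exclusions is not recommended: compassionate-use patients were exempt from them, so it could create a new imbalance, and it needs laboratory and cardiac data that past records may lack.

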3.3.2.1 Inclusion of Minorities and Children

The disorders to be investigated affect both genders and all different ethnic groups and we therefore expect to have proportional representation among the participants of the trials. These are rare disorders, and we will attempt to recruit all presenting potentially eligible patients. Most persons affected with AGS are children and thus pediatric patients will be included.

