5.2.4 AGS Scale

Refer to Appendix 5 for AGS Scale, which will be applied at baseline, 3 months, 6 months, 9 months, 12 months and every subsequent study visit through neurologic exam and conversation with parents.

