6.4 Sample Size and Power

Sample size calculations were performed using PASS 16 sample size software and were based on preliminary data in 35 patients with available data on the AGS scale.

Analysis of the primary outcome, safety data including laboratory studies and adverse events, will be descriptive and include all individuals, available studies and AEs. Power

analysis is not possible for these analyses, since adverse events may be rare, even in the AGS population, and statistical comparisons may not be feasible.

We anticipate that we will have an evaluable sample size of ~45 treated patients. For the analysis of secondary outcomes, in our preliminary analysis when we compared the average of AGS scales prior to treatment (pre-treatment average) to the average of the AGS scale after treatment (post-treatment average), we observed that the average of within subject changes (post-treatment average minus pre-treatment average) was 0.80 (95% CI = 0.45, 1.16) and that the standard deviation of changes was 1.04. This corresponds to an effect-size of 0.80/1.04 = 0.77. From PASS 16, a sample size of 30 data pairs achieves 98.3% power to reject the null hypothesis of zero effect size when the population effect size is 0.77 and the significance level (alpha) is 0.050 using a twosided paired t-test. Should the effect-size be smaller than we observed in our preliminary data, we will have 80% power to detect an effect size of 0.53, which would correspond to an average of within subject changes of 0.55, if the SD of changes is 1.04. We will therefore have sufficient power to detect differences that are similar to those observed in preliminary data. For the more complex analyses that are proposed for the larger data set that contains the historical controls (>50), our power will be even greater.

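### If affected siblings enrol, treating every patient as independent gives wrong standard errors; cluster the variance on family

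*Combined protocol and SAP*

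**What the plan says.** The primary GEE (6.3.2) models time within patients. For the secondary GEE and QLS models, 6.3.3.1 states: "We will fit several working correlation structures to model the association between the repeated measurements on each patient". The Table 2 model with never-treated patients will "use an exchangeable correlation structure to account for the intra- subject correlation of measurements on each patient". The Table 2 paired t-tests and Wilcoxon test take one difference per patient. The ISG and diary analyses (6.3.3.3, 6.3.3.4) reuse these models, and the GMFM-88 model (6.3.3.2) names no level above the patient. Sections 6.3 and 6.4 contain no family identifier, no family clustering and no sibling sensitivity analysis. Genotype appears as a possible covariate in the secondary GEE only.

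On who may enter, 1.1 calls AGS heritable, and later text in the same section calls it Mendelian. Section 3.3.2.1 says "we will attempt to recruit all presenting potentially eligible patients". Sections 3.3.2 and 3.3.3 set no limit per family, and compassionate-use patients enter without meeting those criteria (3.3.1). The AGS scale is scored at baseline, at the listed months and at "every subsequent study visit through neurologic exam and conversation with parents" (5.2.4). The diary is completed by the patient or a proxy (1.5).

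**The concern.** In a heritable childhood disease, more than one affected child per family is foreseeable. Siblings would share a causal genotype and a home. They could also share a parent who knows the treatment and contributes to both children's scores. Positive correlation between their changes is therefore plausible.

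Patient-clustered GEE standard errors, including robust ones, allow for correlation within a patient but not between patients. Every sensitivity analysis in Table 2 makes the same independence assumption, so agreement among them would not reveal a problem. At stake is whether intervals and p-values are correct in a small study that judges results "with a p-value < 0.05 as the criterion for statistical significance" (6.3.1).

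**Working it through.** **1. The plan's own figure.** Section 6.4 says "a sample size of 30 data pairs achieves 98.3% power to reject the null hypothesis of zero effect size", where "the significance level (alpha) is 0.050 using a twosided paired t-test", and "This corresponds to an effect-size of 0.80/1.04 = 0.77". The noncentral t with 29 degrees of freedom and noncentrality 0.77 × √30 = 4.22 gives 98.27%. At effect size 0.53 the noncentrality is 2.90 and power is 80.1%, against the stated 80%. Both figures reproduce, and both assume 30 independent pairs.

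**2. Both siblings treated.** Let N be the number of patients, k the number of sibling pairs and ρ the correlation between siblings' changes. The sum of the changes has variance Nσ² + 2kρσ². Hence true SE / reported SE ≈ √(1 + (2k/N)ρ).

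N = 45 is the expected evaluable sample in 6.4. The documents give neither k nor ρ, so both are assumed. Type I error comes from simulating a one-sample t-test at nominal 5%, with 40,000 or 60,000 runs per cell; the ranges span both sets of runs.

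| Sibling pairs | 2k/N | SE ratio, ρ = 0.3 | SE ratio, ρ = 0.7 | Type I error |
|---|---|---|---|---|
| 3 | 6/45 = 0.133 | √1.040 = 1.020 | √1.093 = 1.046 | 5.4–6.1% |
| 5 | 10/45 = 0.222 | √1.067 = 1.033 | √1.156 = 1.075 | 5.7–6.9% |
| 10 | 20/45 = 0.444 | √1.133 = 1.065 | √1.311 = 1.145 | 6.4–8.7% |

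The ratio says how much larger the true SE is. At 1.145, the reported SE is 1 − 1/1.145 = 12.7% too small.

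**3. Power.** With f = 2k/N, the design effect is 1 + fρ and the effective n is 30 divided by it.
- f = 0.20, ρ = 0.5: design effect 1.10, effective n 27.3, power 97.2% at effect size 0.77 and 76.0% at 0.53.
- f = 0.40, ρ = 0.8: design effect 1.32, effective n 22.7, power 93.9% and 67.5%.

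If 45 patients are evaluable, even the second case leaves 45/1.32 = 34.1, which is above 30. Power is therefore not the main issue.

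**4. A result like the preliminary one.** With mean change 0.80, SD 1.04 and 35 patients (6.4), t = 0.80/(1.04/√35) = 0.80/0.1758 = 4.55. The recomputed interval is 0.44 to 1.16, against the stated 0.45 to 1.16. At f = 0.40 and ρ = 0.8 it becomes 0.39 to 1.21. In the extreme where every patient is in a perfectly correlated pair (design effect 2), t = 4.55/√2 = 3.22, still p < 0.01.

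**5. One sibling treated, the other a historical control.** Take 45 treated and 50 controls (6.4 says more than 50), with m treated children who each have one control sibling. For a simple difference in group means:
- reported variance ∝ 1/45 + 1/50 = 0.0422;
- true variance ∝ 0.0422 − 2mρ/(45 × 50).

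Here ρ is the correlation of the values compared, again assumed. With m = 4.5 (10% of treated) and ρ = 0.2, true/reported SE = √(0.0414/0.0422) = 0.99. With m = 13.5 (30%) and ρ = 0.8, it is √(0.0326/0.0422) = 0.88. The reported SE is then too large.

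**The case against.** The strongest reply is that the documents give no evidence of the problem. No section says that siblings are or will be enrolled, and recruitment also runs through testing laboratories, self-referral and a clinical program (3.1.2.1, 9.6). A reader might infer that the standard errors are wrong as matters stand. The documents do not support that: the point is conditional on siblings enrolling.

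A reader might also infer that error bars are too narrow in every model. Step 5 shows that the error can reverse when siblings fall in different groups.

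The illustration uses a one-sample test. That resembles the Table 2 paired test and the baseline-to-52-week restricted analysis, but not the primary GEE with its time-by-treatment term. It should not be read as the type I error of the primary analysis.

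The correlation that matters for pre/post analyses is between changes, and it may be low. Section 1.5 reports improvement in 6/19, 5/6 and 0/9 patients by baseline level, so siblings at different levels may respond differently. The neurologic exam also contributes to the AGS score alongside the parents. Genotype adjustment may absorb some shared variation in the secondary GEE, and 6.4 describes the secondary analyses as mainly hypothesis-generating.

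All of this limits the size and certainty of the point. It does not remove the gap: the primary model as described has no genotype term, genotype does not capture a shared home or informant, and no analysis in the plan would show whether siblings matter.

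**Conclusion.** The point holds conditionally. If siblings enrol, which the plan neither states nor prevents, patient-level independence gives wrong standard errors in the primary GEE, the secondary GEE/QLS and the paired tests. The direction depends on whether both siblings are treated or one is a control.

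Under the assumed inputs the distortion is modest with 3 to 5 pairs. It becomes material only with about 10 pairs in 45, which would put 44% of patients in sibling pairs and has no basis in the documents.

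A reader might infer that the efficacy conclusion is in danger. Step 4 does not support that for an effect near 0.80 with SD 1.04. The exposure lies in smaller or borderline effects. The change is worth making because it corrects the error in either direction and leaves the results as they are if no siblings enrol.

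**What to change.** In 6.3.2 and 6.3.3:
- Record a family identifier for every treated patient and, where retrievable, every historical control.
- Keep the planned patient-level working correlation structures, but cluster the robust variance of the GEE/QLS models on family, or bootstrap whole families.
- Use family-clustered standard errors for the mean-change tests.
- Report the number of families and sibling sets beside the number of patients.
- Where a control's family link cannot be retrieved, treat that patient as a singleton and say so. The same can apply to lost-to-follow-up compassionate-use patients, whose data are restricted to at most a limited data set (9.7.1).

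Keeping the working structures avoids respecifying the exchangeable and Markov models as nested ones. The cost is one data field, some retrospective look-up for controls, a short addition to the analysis text, and slightly wider intervals if treated siblings are enrolled.
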